## 1. Sample Size Calculation

An a priori power analysis in G\* power with an effect size of 0.5 (Kennedy et al., 2003; Kennedy et al., 2004) indicated that a sample of 130 participants (65 per group, placebo and treatment respectively) with a 10% attrition rate would be necessary to achieve a power level of 0.80 at a significance level of 0.05. Similar trials investigating mood and cognition have shown a change from baseline following an acute dose of lemon balm beginning with changes first observed after 1h and maintained throughout the test day, in samples as small as 18 participants (Kennedy et al., 2004).

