# Primary Outcome Variable

To determine the effect of 300 mg lemon balm on ratings of calmness following a period of cognitive demand, measured using a 9-point Likert Scale, at baseline (0h) and 5 hours post administration. This Calmness 9-point Likert scale is scored from 1, "Not at all Calm" to 9, "Extremely Calm" Calmness Anchor points.

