### **Analysis**

Before analysis, all data will be checked for assumptions of parametric testing, including Normal distribution, then assessed with boxplots to screen for any outliers. On recommendation of a statistician, all repeated measures data will be analysed using Linear Mixed Modelling (LMM) in RStudio v4.0. This technique can be used to model variance relating to both fixed parameters such as experimental doses and random parameters such as individual differences between subjects, within multiple layers of the same model. Models will be adjusted for potential predictive factors, such as sex, diet quality, physical activity level and severity of baseline stress complaints and/or baseline performance on cognitive tasks where the inclusion of these covariates improves the fit of the model, as long as assumptions are met. Subjects will be included as a random factor as a way of controlling for non-independence of data from the same subjects. The models will be applied in a systematic way to retain consistency between analyses. Where possible, an unstructured covariance matrix will be specified for the repeated observations on a subject within the same period. As LMMs do not require balanced data, subjects with missing data points will not be excluded from the analyses. Post-hoc Bonferroni-corrected parametric tests such as independent t-tests will be performed to estimate between-group differences between placebo and intervention groups, or within-group differences between time points, where appropriate.

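### The plan names no deciding between-arm contrast and leaves within-arm tests unconditional, so it does not rule out claiming efficacy because lemon balm changed and placebo did not

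*Combined protocol and SAP*

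**What the plan says.** The Analysis section states that "all repeated measures data will be analysed using Linear Mixed Modelling (LMM) in RStudio v4.0". It gives dose as an example of a fixed effect and makes subject a random effect, but it lists no treatment-by-time term and no primary contrast. It then adds Bonferroni-corrected post-hoc tests, first of differences between the placebo and intervention groups, "or within-group differences between time points, where appropriate". The number of tests in the corrected family is not given, and neither is the rule for choosing one type of test over the other.

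The Primary Outcome Variable section defines the outcome as the effect of lemon balm on calmness, "measured using a 9-point Likert Scale, at baseline (0h) and 5 hours post administration". It does not say whether the arms are compared at 5h, on change from 0h, or in some other way.

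Section 1 sizes the trial "with an effect size of 0.5" at "130 participants (65 per group, placebo and treatment respectively) with a 10% attrition rate", "to achieve a power level of 0.80 at a significance level of 0.05".

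**The concern.** A significant change in one arm beside a non-significant change in the other does not show that the arms differ. Each within-arm test asks whether that arm moved over time, and the randomised comparison is never made. This is true even when each within-arm test uses a correct paired or model-based standard error.

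A change common to both arms is plausible here. Everyone repeats demanding test blocks at 0h, 1h, 3h and 5h, eats lunch, and rates calmness after cognitive demand. If both arms drift by the same modest amount, two separate tests will often disagree by chance. An analyst could follow the plan as written and report that calmness changed on lemon balm but not on placebo as the finding, although the placebo arm exists to prevent that inference.

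**Working it through.** **Step 1. The plan's own sample size.** A two-sample t-test with effect size 0.5 and two-sided alpha 0.05 (sidedness is not stated) needs 64 per group, 128 in total, for 80% power. With 65 per group the power is 80.8%, so 130 fits a between-group comparison with everyone analysed. Adding 10% attrition gives 128 / 0.9 = 142.2, that is 143, or 144 in equal arms, so 130 does not reproduce with attrition included. If 130 is the enrolled number, about 65 × 0.9 = 58.5, say 58, per arm remain, with 76.1% power. That is a separate matter. Here it only means that both 65 and 58 per arm should be tried.

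**Step 2. The formula.** Assume no treatment effect and the same mean change from 0h to 5h in both arms. Let d_z be that common change divided by the SD of the change. Let q be the power of a two-sided paired t-test within one arm (noncentral t, n − 1 degrees of freedom, noncentrality d_z × √n). The arms are independent, so

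P(lemon balm significant, placebo not) = q × (1 − q).

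This is largest at q = 0.5, where it equals 0.25. The documents give no drift; d_z from 0 to 0.6 is an assumption.

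**Step 3. Results.** q is shown for 65 per arm at alpha 0.05; the other columns give the probability that only lemon balm is significant.

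| d_z | q | 65 per arm, 0.05 | 58 per arm, 0.05 | 65 per arm, 0.025 |
|---|---|---|---|---|
| 0 | 0.050 | 4.8% | 4.8% | 2.4% |
| 0.10 | 0.125 | 10.9% | 10.3% | 6.9% |
| 0.20 | 0.355 | 22.9% | 21.8% | 19.0% |
| 0.25 | 0.510 | 25.0% | 24.9% | 23.9% |
| 0.30 | 0.664 | 22.3% | 23.7% | 24.7% |
| 0.40 | 0.888 | 9.9% | 12.8% | 14.7% |
| 0.50 | 0.978 | 2.2% | 3.6% | 4.2% |
| 0.60 | 0.997 | 0.3% | 0.6% | 0.6% |

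Example: at d_z = 0.20, 0.355 × 0.645 = 0.229.

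At d_z = 0 the 4.8% counts changes in either direction; a rise on lemon balm alone is 0.025 × 0.95 = 2.4%. From d_z 0.10 upwards nearly all of the probability lies in the direction of the drift. If calmness falls over the day, the pattern that flatters lemon balm is a significant fall on placebo alone, which has the same probability.

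**Step 4. Bonferroni.** Correction lowers q at a given drift but not the ceiling of q × (1 − q). With 65 per arm the 25% peak moves from d_z 0.25 (uncorrected) to 0.28 for two tests, 0.30 for three, 0.32 for four and 0.34 for six.

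**Step 5. The comparator.** A two-sided 0.05 between-arm test on change has a 5% false-positive rate whatever the common drift (4.9–5.1% in simulations of 200,000 trials per setting). Half of that, 2.5%, favours lemon balm. If the lemon-balm-only pattern counted only when the between-arm test was also significant, it would occur in at most about 2.4% of null trials.

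**The case against.** The strongest reply is that the mixed model is the main analysis and the clause concerns only post-hoc tests. On an ordinary reading, the follow-up suits the effect found: between groups for a treatment effect, between time points for a time effect. The sample size is consistent with a two-group comparison, and the heart-rate and blood-pressure outcome is framed as intervention against placebo. So a reader who infers that the plan puts within-arm tests in place of the between-arm test goes too far; no section says that a within-arm change decides efficacy. What stands is that this ordering is not written down. No model term is named as decisive, and nothing makes the within-arm tests wait for it.

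A reader might also take Section 1's remark that similar trials "have shown a change from baseline following an acute dose of lemon balm" as a sign that this trial will infer from within-arm change. It is background on earlier work, not an analysis rule, and changes from baseline can themselves be compared between conditions.

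Thirdly, a quarter of null trials might be read as the expected error rate. It is a ceiling. It needs an analyst who relies on the within-arm pattern and a common drift near 0.25 SD of change. With no drift the rate is about 5%, with a large drift it is lower still, and Bonferroni reduces it at small drifts: with six tests (family size assumed) it is 0.8% at d_z 0 and 3.1% at 0.10.

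Lastly, banning within-arm p-values altogether is a reporting preference. Naming the deciding contrast removes the bias without it.

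**Conclusion.** The concern holds as a gap in the plan: it does not rule out concluding efficacy from a change on lemon balm and none on placebo. The size rests on four assumptions: that the within-arm rule is used, that there is no treatment effect, that both arms share a drift, and that 65 per arm are analysed at two-sided 0.05. The false claim then arises in about 5% of trials with no drift, 10–25% for d_z 0.10–0.40, and about 2% or less from 0.5 upwards, against 2.5% for a false result favouring lemon balm from a between-arm test. With 58 per arm the picture is much the same. If the authors intend within-arm tests only after a significant between-arm result, the inflation disappears, but that has to be stated. The change should be made before the data are unblinded.

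**What to change.** Replace the within-group clause in the Analysis section with wording such as:

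> The conclusion on the primary outcome rests on the between-arm difference in calmness at 5h, adjusted for baseline, from the mixed model. Conclusions on other outcomes also rest on between-arm model contrasts. Within-arm changes are descriptive, shown as means with confidence intervals, and are not evidence of a treatment effect.

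The treatment-by-time contrast from 0h to 5h is an acceptable alternative. Under randomisation it targets the same between-arm effect, but the estimate may differ slightly, so the plan should name one of the two in advance.

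The cost is a few sentences of text, with no extra participants, visits or data. Within-arm means are still reported. The one thing given up is that within-arm results can no longer support an efficacy claim.
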